1.3.2 Potential Risks to Subjects

As with any vaccine, it is important to note that vaccination with QIV-HD may not protect all recipients against the disease it is designed to prevent (i.e., influenza). See below for other potential risks.

Possible Reactions to Blood Draw

Venipuncture causes transient discomfort and may cause temporary hypotension from a vasovagal response (e.g., fainting). If pressure is not applied long enough to the venipuncture site, bruising

due to bleeding beneath the skin may occur. Infection at the site of needle insertion could theoretically occur but is exceedingly rare when the standard sterile technique is utilized.

Possible Reactions to Vaccination

Vaccine injection into the deltoid muscle causes transient discomfort. Immediate and potentially life-threatening allergic reactions to the vaccine could be manifested by adverse events (AEs) such as laryngeal edema, asthma, or hypotension. These types of reactions are exceedingly rare and would most likely occur in persons with a severe reaction to influenza vaccine in the past.

The rate of injection site reactions is expected to be higher with the SC route compared to the IM route due to the fact that the inflammatory reactions induced by the vaccines are closer to the surface of the skin and therefore more visible to direct examination.

Post-marketing Experience with TIV-HD (Fluzone High Dose)

The following events have been spontaneously reported during the post-approval use of TIV-HD. These events are reported voluntarily from a population of uncertain size, consequently it is not always possible to reliably estimate the frequency of the events or establish a causal relationship to vaccine exposure. AEs were included based on one or more of the following factors: intensity, frequency of reporting, or strength of evidence for a causal relationship to TIV-HD.

Events reported spontaneously during post-approval use of TIV-HD and may occur in subjects receiving QIV-HD are:

- Blood and Lymphatic System Disorders: thrombocytopenia, lymphadenopathy
- Immune System Disorders: anaphylaxis, other allergic/hypersensitivity reactions (including angioedema)
- Eye Disorders: ocular hyperemia
- Nervous System Disorders: Guillain-Barré syndrome, convulsions, febrile convulsions, myelitis (including encephalomyelitis and transverse myelitis), facial palsy (Bell's palsy), optic neuritis/neuropathy, brachial neuritis, syncope (shortly after vaccination), paresthesia

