6.1.1.2 Preparation and Administration

The investigational QIV-HD is prepared by an unblinded administrator (a designated study staff such as an Investigator/Sub-investigator, or a nurse), or the designated pharmacist and administered intramuscularly into the upper arm (deltoid area) by the unblinded administrator

without the presence of any other study staffs who may be an assessor for safety in subsequent visits.

The subjects are blinded with eye mask or other appropriate methods during administration.

Vaccination is not to be performed in subjects allergic to one of the constituents of the vaccine.

Prior to administration, all study products must be inspected visually for cracks, broken seals, correct label content (see [Section 6.3.1](#)), and extraneous particulate matter and/or discoloration, whenever solution and container permit. If any of these conditions exists, the vaccine must not be administered. A replacement dose is to be used, and the event is to be reported to the Sponsor.

Subjects must be kept under observation for 30 minutes after vaccination to ensure their safety, and any reactions during this period will be documented in the CRB. Appropriate medical equipment and emergency medications, including epinephrine (1:1000), must be available on site in the event of an anaphylactic, vasovagal, or other immediate allergic reaction.

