6.1.2.2 Preparation and Administration

The control product is administered subcutaneously into the upper arm (posterior region).

The procedures for preparing and administering the control product are the same as those described for the study product in [Section 6.1.1.2](#).

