9.2.2.3.2 Reactogenicity (Solicited Reactions From Day 0 to Day 7 After Vaccination)

After vaccination, subjects will be provided with a diary card, a digital thermometer, and a flexible ruler, and will be instructed how to use them. The following items will be recorded by the subjects in the diary card on the day of vaccination and for the next 7 days (i.e., D0 through D7) until resolution:

- Daily temperature, with the route by which it was taken
- Daily measurement or intensity grade of all other solicited injection site and systemic reactions
- Action taken for each event (e.g., medication)

The action(s) taken by the subject to treat and/or manage any solicited reactions will be classified in the CRB using the following list (all applicable items should be checked):

- None
- Medication
- Health care provider contact
- Hospitalized

Subjects will be contacted by telephone 8 days (+2 days) after vaccination to remind them to record all safety information in the diary card.

If the timing of the telephone call should fall on a weekend or a holiday, the call should be made on the next business day. If contact is not made on the designated day, site staff will continue

calling until contact is made. Every telephone attempt and its outcome will be documented in the source document.

Table 1 and **Table 2** present, respectively, the injection site reactions and systemic reactions that are prelisted in the diary cards and CRB, together with the intensity scales.

Table 1 - Solicited Injection Site Reactions: Terminology, Definitions, and Intensity Scales

CRB term (MedDRA lowest level term [LLT])	Injection site pain	Injection site erythema	Injection site swelling	Injection site induration	Injection site bruising
Diary card term	Pain	Redness	Swelling	Hardening	Bruising

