Definition	Pain either present spontaneously or when the injection site is touched or injected limb is mobilized	Presence of a redness including the approximate point of needle entry	Swelling at or near the injection site Swelling or edema is caused by a fluid infiltration in tissue or cavity and, depending on the space available for the fluid to disperse, swelling may be either soft (typically) or firm (less typical) to touch and thus can be best described by looking at the size of the swelling	Hardening at or near the injection site. Hardening is caused by a slow diffusion of the product in the tissue leading to a thick or hard area to touch at or near the injection site and thus can be best described by looking at the size of the hardening.	Bruising is the result of the diffusion of blood in the skin from ruptured blood vessels that forms a purple or black and blue spot on the skin. It can be best described by looking at its size.

CRB term (MedDRA lowest level term [LLT])	Injection site pain	Injection site erythema	Injection site swelling	Injection site induration	Injection site bruising
Intensity scale ^a	
CRB:
 
Grade 1: A type of adverse event that is usually transient and may require only minimal treatment or therapeutic intervention. The event does not generally interfere with usual activities of daily living.
 
Grade 2: A type of adverse event that is usually alleviated with additional therapeutic intervention. The event interferes with usual activities of daily living, causing discomfort but poses no significant or permanent risk of harm to the research participant.
 
Grade 3: A type of adverse event that interrupts usual activities of daily living, or significantly affects clinical status, or may require intensive therapeutic intervention.
 
Diary card/eDC:
 
Grade 1: No interference with usual activities
 
Grade 2: Some interference with usual activities
 
Grade 3: Significant; prevents usual activities
	
Grade 1: ≥ 25 to ≤ 50 mm
 
Grade 2: ≥ 51 to ≤ 100 mm
 
Grade 3: > 100 mm
			

^a For the subjective reaction of pain, subjects will record the intensity level (Grade 1, 2, or 3) in the diary card. For the measurable reactions of redness and swelling, they will record just the size of the reaction, and the classification as Grade 1, 2, or 3 will be assigned at the time of the statistical analysis

Table 2 - Solicited Systemic Reactions: Terminology, Definitions, and Intensity Scales

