### ***Presence***

Presence is derived from the maximum intensity of the period considered:

- No presence : None
- Presence : Grade 1, Grade 2 or Grade 3
- Unknown or Missing presence : Missing

Subjects with at least one non-missing presence for a specific endpoint will be included in the analysis. Conversely, those without a non-missing presence will not be included in the analysis of the endpoint.

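### Visible local reactions are self-measured at different arm sites in the two groups, so they may be ascertained unequally, in a direction the documents do not settle

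*Protocol*

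**What the plan says.** **Injection site.** QIV-HD is "administered intramuscularly into the upper arm (deltoid area) by the unblinded administrator" (Protocol 6.1.1.2). For QIV-SD, Protocol 6.1.2.2 states: "The control product is administered subcutaneously into the upper arm (posterior region").

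**Who measures.** Under Protocol 9.2.2.3.2, "subjects will be provided with a diary card, a digital thermometer, and a flexible ruler, and will be instructed how to use them". The same section continues: "The following items will be recorded by the subjects in the diary card on the day of vaccination" and for the next 7 days. The items include "Daily measurement or intensity grade of all other solicited injection site and systemic reactions". Footnote a to Table 1 adds: "For the measurable reactions of redness and swelling, they will record just the size of the reaction". The grade is assigned at analysis. SAP 5.4.2.1 treats erythema, swelling, induration and bruising all as measurable, and grades them by size from 25 mm upwards.

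**Staff contact.** There is a 30-minute observation on D0, a telephone call at D8, and V02 at D28 to D35, where an examination is made only if needed (Protocol 9.2.2.3, 9.2.2.3.1, 9.2.2.3.2). Staff who collect safety data do not know the vaccine or the route (Protocol 6.4).

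**Visibility by route.** Protocol 1.3.2 expects more injection site reactions by the SC route because they are "closer to the surface of the skin and therefore more visible to direct examination".

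**Derivation.** SAP 5.4.2.1: "Presence is derived from the maximum intensity of the period considered". *Unknown* is treated as *Missing*. If the investigator records presence as *No* and all daily records are missing, every day becomes *None*.

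**The concern.** The same ruler and diary are used on two different parts of the arm, and the part is fixed by treatment group. A person sees and measures the deltoid area of their own arm more easily than the back of it. That is an inference from ordinary anatomy, not a statement in the documents. If it holds, a reaction on the posterior arm may be missed or read too small, and blinded staff cannot adapt their advice to the site.

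The exposure is mainly the presence of erythema and bruising, and the measured size of swelling and hardening. Pain is not affected, and swelling and hardening can be felt.

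At stake is the side-by-side reading of local reaction rates under the secondary safety objective. Protocol 5.1.2 blinds subjects and safety assessors in order to limit bias in that assessment. Unequal ascertainment is not reduced by a larger sample, and no field described in the documents would reveal it afterwards.

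**Working it through.** **1. The plan's own figure.** The documents give no expected local reaction rate and no detection rate, so there is nothing of that kind to reproduce. The one design figure is the 90% overall power. With 5% attrition, 1050 × 0.95 = 997.5, so 997 per arm. Power per strain is above 0.9999 for GMT (ratio 1.6, SD 0.7) and for 40% vs 57%, and 0.948 for 50% vs 58%. Treating the tests as independent, the product is about 0.948² ≈ 0.899, or 0.901 with the Newcombe interval simulated. The stated 90% reproduces. It uses no safety data, so this point leaves it untouched.

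**2. How a missed or partial reading passes through SAP 5.4.2.1.**

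- Reaction not noticed, subject records nothing present: *None*, then no presence.
- Reaction of 25 mm or more read as under 25 mm: *None*.
- Card blank or *Unknown* on every day, investigator presence *No*: every day *None*, then no presence.
- Card blank or *Unknown* on every day, investigator presence not *No*: *Missing*, and the subject leaves that endpoint's analysis.

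The third path turns a site that was never inspected into a confirmed non-reaction.

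**3. Illustration of size.** Assumptions, none from the documents: equal true rate p in both arms, full detection with QIV-HD, and a proportion m of visible QIV-SD reactions missed or read too small. The 1050 per arm is from Protocol 5.1.1.

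- Observed QIV-SD rate = p(1 − m)
- False gap = p × m
- Half-width = 1.96 × √{[p₁(1 − p₁) + p₂(1 − p₂)]/1050}

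For p = 10% and m = 30%: observed QIV-SD rate 0.10 × 0.70 = 7%; gap 3 points; half-width 1.96 × √[(0.0900 + 0.0651)/1050] = 2.4 points.

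| True rate | Missed | Observed QIV-SD | False gap (points) | Half-width (points) |
|---|---|---|---|---|
| 10% | 10% | 9% | 1 | 2.5 |
| 10% | 20% | 8% | 2 | 2.4 |
| 10% | 30% | 7% | 3 | 2.4 |
| 20% | 10% | 18% | 2 | 3.4 |
| 20% | 20% | 16% | 4 | 3.3 |
| 20% | 30% | 14% | 6 | 3.2 |
| 30% | 10% | 27% | 3 | 3.9 |
| 30% | 20% | 24% | 6 | 3.8 |
| 30% | 30% | 21% | 9 | 3.7 |

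The half-width is only a yardstick. The plan gives Clopper-Pearson intervals within each group for safety and no between-group test.

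**4. Why the sign is open.** If nearness to the skin surface raises SC detection by a factor g relative to IM, relative detection is g(1 − m). The two effects cancel at g = 1/(1 − m), which is 1.11, 1.25 and 1.43 for m = 10%, 20% and 30%. The documents give neither g nor m.

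**The case against.** The case against is substantial. No passage says that the posterior arm is harder to see, and the only passage on visibility by route points the other way. Every subject gets a ruler and instruction in its use. Protocol 11.1 gives consistent reporting as the aim of that instruction and has staff clarify unclear entries, Protocol 13.2 requires clarification of missing or discrepant diary data, and Protocol 9.2.2.1 makes investigator assessment of solicited reactions mandatory. The diary card is not among the documents, so it may already cover the matter. The SAP has a *Missing* category. The loss rates are hypothetical, and at 10% loss the false gap stays inside the half-width at all three rates. Safety is descriptive.

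Most of this stands and limits the point. Three parts do not dispose of it:

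- Protocol 1.3.2 concerns depth and direct examination. No direct examination is scheduled on D1 to D7, so it offsets the site effect to an unknown degree and does not exclude it.
- Instruction in using a ruler is not instruction in inspecting a site out of view. Clarification at D28 to D35 cannot recover a size that was never measured.
- The *Missing* category is not a full safeguard, because an investigator *No* with all daily records missing overrides it.

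A diary tick cannot catch a reaction that the subject believes is absent. That is why the inspection instruction matters more than the tick.

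**Conclusion.** The point holds as possible differential ascertainment of visible local reactions, of unknown net direction and size. It rests on three documented facts (different sites by arm, self-measurement, no scheduled staff measurement on D1 to D7) and one inference (a site behind the arm is harder to inspect). Under the illustrative 10% to 30% loss, the false gap is 1 to 3 points at a true rate of 10% and 2 to 6 points at 20%. It exceeds the half-width only towards the upper end of that range.

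A reader might infer more than the documents support:

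- *QIV-SD is under-counted.* Not established; Protocol 1.3.2 points to greater SC visibility.
- *QIV-HD will look more reactogenic than it is.* A loss confined to QIV-SD leaves QIV-HD's own rate and interval unchanged; only the contrast could shift.
- *Subjects measure without anyone to help.* The documents say nothing about living situation or help at home.
- *Four of the five local endpoints are equally exposed.* Swelling and hardening can be detected by touch.

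The primary immunogenicity objective, type I error and power are not affected. This is a cheap improvement, not a flaw in the main conclusion.

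**What to change.** In Protocol 9.2.2.3.2 and the diary card instructions, tell every subject in both arms to inspect and measure the whole upper arm each day, using a mirror or another person's help if needed. Add a daily option that the site could not be seen or measured. Identical wording in both arms preserves the blind.

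In SAP 5.4.2.1, keep such days as *Missing*, and exempt them from the rule that turns investigator presence *No* with all daily records missing into *None*. SAP 5.4.4 already allows the number with missing data to be shown, so the use of this option could be reported by arm.

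The cost is one instruction, one diary option and one SAP line, with slightly more diary burden and a few more missing days.

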9.2.2.3.3 Unsolicited Adverse Events

In addition to recording solicited reactions, subjects will be instructed to record any other medical events that may occur during the 28-day period after vaccination. Space will be provided in the diary card for this purpose. Information on SAEs will be collected and assessed throughout the study, from inclusion until 28 days (+ 7 days) after vaccination. Any SAE occurring at any time during the study will be reported by the Investigator in the CRB according to the completion instructions provided by the Sponsor; this includes checking the “Serious” box on the AE CRF and completing the appropriate Safety Complementary Information CRFs. All information concerning the SAE is to be reported either as part of the initial reporting or during follow-up reporting if relevant information became available later (e.g., outcome, medical history, results of investigations, copy of hospitalization reports). See [Section 10](#) for further details on SAE reporting.

For each unsolicited AE (whether serious or non-serious), the following information is to be recorded:

- Start and stop dates¹¹
- Intensity of the event:

For measurable unsolicited AEs that are part of the list of solicited reactions, the size of the AE as well as the temperature for fever will be collected and analyzed based on the corresponding scale used for solicited reactions (see [Table 1](#) and [Table 2](#)).

All other unsolicited AEs will be classified according to the following intensity scale:

- Grade 1: A type of AE that is usually transient and may require only minimal treatment or therapeutic intervention. The event does not generally interfere with usual activities of daily living.
- Grade 2: A type of AE that is usually alleviated with additional therapeutic intervention. The event interferes with usual activities of daily living, causing

¹¹ The stop date of all related AEs will be actively solicited. For other events, the investigator will provide the stop date when it becomes available. AEs for which no stop date was obtained during the course of the study will be considered as ongoing at the end of the study.

discomfort but poses no significant or permanent risk of harm to the research participant.

- Grade 3: A type of AE that interrupts usual activities of daily living, or significantly affects clinical status, or may require intensive therapeutic intervention.
- Whether the AE was related to the IP (for unsolicited systemic AEs)

The Investigator will assess the causal relationship between the AE and the IP as either “Not related” or “Related”, as described in [Section 9.2.2.3.5](#).

- Action taken for each AE (e.g., medication)

The action(s) taken by the subject to treat and/or manage any unsolicited AEs will be classified in the CRB using the following list (all applicable items should be checked):

- None
- Medication
- Health care provider contact
- Hospitalized
- Whether the AE was serious

For each SAE, the investigator will complete all seriousness criteria that apply (outcome, elapsed time, and relationship to study procedures)

- Whether the AE caused study discontinuation

9.2.2.3.4 Adverse Events of Special Interest

AESIs will be captured as SAEs (collected throughout the study). These include new onset of [\(31\)](#):

- Guillain-Barré syndrome
- encephalitis/myelitis (including transverse myelitis)
- Bell’s palsy
- optic neuritis
- brachial neuritis

9.2.2.3.5 Assessment of Causality

The Investigator will assess the **causal relationship** between each unsolicited systemic AE and the product administered as either **not related** or **related**, based on the following definitions^{[12](#)}:

¹² ICH Guidelines, Clinical Safety Data Management E2A

Not related – The AE is clearly / most probably caused by other etiologies such as an underlying condition, therapeutic intervention, or concomitant therapy; or the delay between vaccination and the onset of the AE is incompatible with a causal relationship; or the AE started before the vaccination (screening phase, if applicable).

Related – There is a “reasonable possibility” that the AE was caused by the product administered, meaning that there is evidence or arguments to suggest a causal relationship.

Note: By convention, all AEs reported at the injection site (whether solicited or unsolicited) and all solicited systemic AEs are considered to be related to the administered product and therefore are referred to as reactions and do not require the Investigator’s opinion on relatedness.

AEs likely to be related to the product, whether serious or not, that persist at the end of the study will be followed up by the Investigator until their complete disappearance or the stabilization of the subject’s condition. The Investigator will inform the Sponsor of the date of final disappearance of the event or the date of “chronicity” establishment.

9.2.3 Efficacy

No clinical efficacy data will be obtained in the study.

9.3 OBSERVATIONAL ENDPOINTS AND ASSESSMENT METHODS

There are no observational objectives in this study.

10 REPORTING OF SERIOUS ADVERSE EVENTS

To comply with current regulations on SAE reporting to health authorities, the Investigator must document all SAEs regardless of causal relationship, and notify the Sponsor within the notification timelines stated in the following sections. The Investigator will give access and provide the Sponsor with all necessary information to allow the Sponsor to conduct a detailed analysis of the safety of the IPs. It is the responsibility of the Investigator to request all necessary documentation (e.g., medical records, discharge summary, physical autopsy report if performed) in order to provide comprehensive safety information. All relevant information must then be transcribed onto the AE CRF and the appropriate Safety Complementary Information CRFs.

10.1 REPORTING BY THE INVESTIGATOR

In the case of a SAE, the Investigator or any designees must immediately:

- ENTER (within 24 hours) the information related to the SAE in the appropriate screens of the CRB; the system will automatically send the notification to the Sponsor after approval by the Investigator within the CRB or after a standard delay.
- SEND (preferably by fax or e-mail) the photocopy of all examinations carried out and the dates on which these examinations were performed, to the representative of the monitoring team whose name, fax number, and e-mail address appear on the clinical study protocol. Care should be taken to ensure that the subject's identity is protected and the subject's identifiers in the clinical study are properly mentioned on any copy of source document provided to the Sponsor. For laboratory results, include the laboratory normal ranges.
- All further data updates should be recorded in the CRB as appropriate, and further documentation as well as additional information (for laboratory data, concomitant medication, subject status, etc.) should be sent (by fax or e-mail) to the monitoring team within 24 hours of knowledge. In addition, any effort should be made to further document within the week (7 days) following initial notification any SAE that is fatal or life threatening.
- A back-up plan is used (using paper flow) when the CRB system does not work.

Back-up plan

- SEND (within 24 hours, preferably by fax or e-mail) the signed and dated corresponding page(s) in the CRB to the representative of the monitoring team whose name, fax number, and e-mail address appear on the clinical study protocol.
- ATTACH the photocopy of all examinations carried out and the dates on which these examinations were performed. Care should be taken to ensure that the subject's identity is protected and the subject's identifiers in the clinical study are properly mentioned on any

copy of source document provided to the Sponsor. For laboratory results, include the laboratory normal ranges.

- All further documentation should be sent to the monitoring team within 24 hours of knowledge. In addition, every effort should be made to further document within the week (7 days) following initial notification any SAE that is fatal or life threatening.

Any SAE brought to the attention of the Investigator at any time after the end of the study for the subject and considered by the Investigator to be caused by the IP with a reasonable possibility, should be reported to the monitoring team.

